#### **8.6.** Quality Control and Quality Assurance

Quality control and quality assurance will be performed according to Covance standard operating procedures or per client request, and as applicable, according to the contract between Covance and the Sponsor.

#### 9. ADMINISTRATIVE ASPECTS

## 9.1. Change in Protocol

There will be no alterations in the protocol without agreement between the Sponsor and the Investigator (or designee).

There will be no alterations in the protocol affecting subject safety without the express written approval of the Sponsor, Investigator (or designee), and the IRB (see Form FDA 1572).

# 9.2. Site Initiation Visit/Investigator Meeting

Prior to the start of the clinical study, the representative(s) of the Sponsor will meet with the Investigator (or designee) and appropriate CRU staff to familiarize the Investigator (or designee) and CRU staff with the materials necessary for conducting the clinical study.

#### 9.3. Disclosure

All information provided regarding the study, as well as all information collected/documented during the study, will be regarded as confidential. The Investigator (or designee) agrees not to disclose such information in any way without prior written permission from the Sponsor.

Any publication of the results, in part or in total (eg, articles in journals or newspapers, oral presentations, abstracts) by the Investigator (or designee) or their representative(s), shall require prior notification and review, within a reasonable timeframe, by the Sponsor, and cannot be made in violation of the Sponsor's confidentiality restrictions or to the detriment of the Sponsor's intellectual property rights.

#### 9.4. Monitoring

The Sponsor will designate a Study Monitor who will be responsible for monitoring this clinical trial. The Sponsor's Study Monitor will monitor the study conduct, proper eCRF and source documentation completion and retention, and accurate study drug accountability. To this end, the Sponsor's Study Monitor will visit the CRU at suitable intervals and be in frequent contact through verbal and written communication. It is essential that the Sponsor's Study Monitor has access to all documents (related to the study and the individual participants) at any time these are requested. In turn, the Sponsor's Study Monitor will adhere to all requirements for subject confidentiality as outlined in the ICF. The Investigator (or designee) and Investigator's staff will be expected to cooperate with the Sponsor's Study Monitor, to be available during a portion of the monitoring visit to answer questions, and to provide any missing information.

#### 9.5. Institutional Review Board

In accordance with US Title 21 Code of Federal Regulations (CFR) 56, the protocol, advertisement, ICF, and other information provided to subjects will be reviewed and approved by the IRB. The Sponsor will supply relevant material for the Investigator (or designee) to submit to the IRB for the protocol's review and approval. Verification of the

Protocol CONFIDENTIAL

Covance Study: 8425120 Protocol Reference: LOXO-BTK-20016

IRB's unconditional approval of the protocol and the written ICF statement will be transmitted to the Investigator (or designee).

The IRB will be informed by the Investigator (or designee) of subsequent protocol amendments and of serious and unexpected AEs. Approval for protocol amendments will be transmitted in writing to the Investigator (or designee). If requested, the Investigator (or designee) will permit audits by the IRB and regulatory inspections by providing direct access to source data/documents.

The Investigator (or designee) will provide the IRB with progress reports at appropriate intervals (not to exceed 1 year) and a Study Progress Report following the completion, termination, or discontinuation of the Investigator's (or designee's) participation in the study.

#### 9.6. Informed Consent

Written informed consent for the study will be obtained from all subjects before protocol-specific procedures are carried out. The ICF will be approved (along with the protocol) by the IRB and will be acceptable to the Sponsor.

The Investigator (or designee) will explain the nature of the study and the action of the test product. The subjects will be informed that participation is voluntary and that they can withdraw from the study at any time. In accordance with 21 CFR 50, the informed consent process shall be documented by the use of a written ICF approved by the IRB and signed by the subject prior to protocol-specific procedures being performed.

The subject will sign 2 copies of the ICF. One copy will be given to the subject, and the other will be maintained with the subject's records.

#### 9.7. Records

The results from data collected at Screening and during the study will be recorded in the subject's eCRF. To maintain confidentiality, the subjects will be identified only by numbers.

The completed eCRFs will be transferred to the Sponsor (or designee). Copies of each eCRF will be retained by the Investigator (or designee). All source documents, records, and reports will be retained by the CRU in accordance with 21 CFR 312.62(c).

All primary data, or copies thereof (eg, laboratory records, eCRFs, data sheets, correspondence, photographs, and computer records), which are a result of the original observations and activities of the study and are necessary for the reconstruction and evaluation of any study report, will be retained in the CRU archives.

#### 9.8. Reference to Declaration of Helsinki/Basic Principles

The study procedures outlined in this protocol will be conducted in accordance with the US CFR governing Protection of Human Subjects (21 CFR 50), Financial Disclosure by Clinical Investigators (21 CFR 54), IRBs (21 CFR 56), Investigational New Drug Application (21 CFR 312), Applications for FDA Approval to Market a New Drug (21 CFR 314), and Radioactive Drugs for Certain Research Uses (21 CFR 361.1), as appropriate. As such, these sections of US Title 21 CFR, along with the applicable International Council for

Harmonisation (ICH) Guidelines, are commonly known as Good Clinical Practices, which are consistent with the Declaration of Helsinki.

# 9.9. Financing and Insurance

Financing and insurance will be addressed in a separate agreement.

# 11. APPENDICES

## **Appendix 1: Adverse Event Reporting**

#### **Adverse Events**

#### Definition of Adverse Events

An adverse event (AE; or adverse experience) is defined as any untoward medical occurrence experienced by a patient or healthy adult subject, whether or not considered drug-related by the Investigator (or designee). A treatment-emergent AE is an AE that starts on or after the first administration of study drug.

The following are all AEs:

- unfavorable changes in general condition;
- subjective or objective signs/symptoms;
- concomitant diseases or accidents;
- clinically significant adverse changes in laboratory parameters observed in a subject during a clinical study.

AEs comprise all disturbances of general health status, subjective and objective disease symptoms (including laboratory abnormalities that are deemed clinically significant by the Investigator [or designee]), and accidents observed in the context of a clinical trial, irrespective of a possible causal relationship with the administration of the trial substance.

## Categorization of AEs

The severity of AEs will be categorized based on the National Cancer Institute Common Terminology Criteria for Adverse Events (CTCAE) Version 5.0 as follows:

- **Grade 1 Mild:** Asymptomatic or mild symptoms; clinical or diagnostic observations only; intervention not indicated
- **Grade 2 Moderate:** Minimal, local, or noninvasive intervention indicated; limiting age-appropriate instrumental Activities of Daily Living (ADL)\*
- Grade 3 Severe or medically significant but not immediately life-threatening: Hospitalization or prolongation of hospitalization indicated; disabling; limiting self-care ADL\*\*
- **Grade 4 Life-threatening consequences:** An event that puts the subject at immediate risk of death
- **Grade 5:** Death related to AE.

Note: Not all grades are appropriate for all AEs. Therefore, some AEs are listed within the CTCAE with fewer than 5 options for grade selection. Grade 5 (death) is not appropriate for some AEs and therefore is not an option.

\* Instrumental ADL refer to preparing meals, shopping for groceries or clothes, using the telephone, managing money, etc.

\*\*Self-care ADL refer to bathing, dressing and undressing, feeding self, using the toilet, taking medications, and not bedridden.

The Investigator (or designee) will make a determination of the relationship of the AE to the study drug using a 2-category system according to the following guidelines:

- **NOT RELATED** = The time course between the administration of investigational product and the occurrence or worsening of the AE rules out a causal relationship and another cause (eg, concomitant drugs, therapies, complications, comorbidities) is suspected.
- **RELATED** = The time course between administration of investigational product and the occurrence or worsening of the AE is consistent with a causal relationship and no other cause (eg, concomitant drugs, therapies, complications, comorbidities) can be identified.

An AE is associated with the use of the drug if there is a reasonable possibility that the experience may have been caused by the drug.

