# 4.6. Removal of Subjects from Study Participation

Subjects will be informed that they are free to withdraw from the study at any time and for any reason. The Investigator (or designee) may remove a subject from the study if, in the Investigator's (or designee's) opinion, it is not in the best interest of the subject to continue the study. Subjects may be withdrawn because of the following:

 change in compliance with inclusion/exclusion criterion that is clinically relevant and affects subject safety

- occurrence of AEs
- occurrence of pregnancy
- non-compliance with study restrictions

Notification of withdrawal will immediately be made to the Sponsor. In case of withdrawal, efforts will be made to perform all final study day assessments (Appendix 4). The date the subject is withdrawn from the study and the reason for withdrawal will be recorded on the subject's electronic Case Report Form (eCRF). All withdrawn subjects with AEs that are assessed as related to study drug and which are ongoing at ET may continue to be followed until the symptoms or value(s) return to normal, or acceptable levels, as judged by the Investigator (or designee) and confirmed by the Sponsor.

The entire study may be discontinued at the discretion of the Investigator (or designee) or Sponsor, based on the occurrence of the following:

- AEs unknown to date with respect to their nature, severity, and/or duration;
- increased frequency and/or severity and/or duration of known AEs;
- medical or ethical reasons affecting the continued performance of the study;
- difficulties in the recruitment of subjects;
- cancellation of drug development.

In the event that the study is terminated early, the Sponsor or its designee will provide specific guidance to the CRU regarding the EOS procedures.

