#### **7.2.1.** Adverse Events

AE definitions; assignment of severity, causality, action taken, and outcome; and procedures for reporting SAEs are detailed in Appendix 1.

Subjects will be asked a non-leading HDYF? Question such as "Have there been any changes in your health status since Screening/since you were last asked?" at the timepoints specified in Appendix 4 (ie, at Screening [after the ICF is signed], at Check-in [Day -1], at each postdose vital sign measurement, and at an appropriate time for all other days). Subjects will also be encouraged to voluntarily report AEs occurring at any other time through the EOS.

Covance Study: 8425120 Protocol Reference: LOXO-BTK-20016

AEs, whether volunteered, identified by the subject's responses to HDYF? Inquiries, or noted on physical examination, ECG, vital sign measurements, or clinical laboratory evaluations, will be recorded throughout the study (ie, from signing of the ICF until EOS [or ET if the subject discontinues from the study and does not complete a follow-up phone call]), either as subject medical history (if the event is reported as beginning prior to signing of the ICF or if the event occurs prior to study drug administration on Day 1 and is assessed as not related to study procedures by the Investigator [or designee]) or as AEs (if the event occurs after signing of the ICF but prior to study drug administration on Day 1 and is assessed as related to study procedures by the Investigator [or designee], or if the event occurs after study drug administration on Day 1 through EOT or ET regardless of relationship to study drug). From EOT or ET through EOS, only AEs assessed as related to study drug by the Investigator (or designee) are to be reported. All SAEs that develop from the time of ICF signing until EOS (or ET, if the subject discontinues from the study and does not complete a follow-up phone call) are to be reported.

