Unless a subject withdraws consent or is withdrawn from the study and does not complete the follow-up phone call, all subjects must be followed until EOS. Subjects with AEs that are assessed as related to study drug by the Investigator (or designee) which are ongoing at EOS may continue to be followed until the symptoms or value(s) return to normal, or acceptable levels, as judged by the Investigator (or designee) and confirmed by the Sponsor. The Investigator (or designee) should use appropriate judgment in ordering additional tests as necessary to monitor the resolution of events. The Sponsor may request that additional safety tests be performed.

Subjects will receive a follow-up phone call 7 days ( $\pm$  2 days) after EOT or ET to determine if any SAE or drug-related AE has occurred since the EOT or ET visit.

At all times, a subject may be required to remain at the CRU for longer at the discretion of the Investigator (or designee).

Any event that meets the criteria of a suspected unexpected serious adverse reaction (SUSAR) will be reported to the Institutional Review Board (IRB) according to CRU policy by the Investigator (or designee) and to regulatory authorities by the Sponsor (or Sponsor designee) according to regulatory authority requirements. Refer to Reference Safety Information in the current IB for LOXO-305 for additional safety information.

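### The RELATED and NOT RELATED definitions in Protocol Appendix 1 are not complements: an AE with consistent timing and an identified alternative cause fits neither, and RELATED is stricter than the section's own reasonable-possibility test

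*Protocol*

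**What the plan says.** Under Categorization of AEs in Protocol Appendix 1, the investigator "will make a determination of the relationship of the AE to the study drug using a 2-category system according to the following guidelines". An AE is RELATED when its time course "is consistent with a causal relationship and no other cause (eg, concomitant drugs, therapies, complications, comorbidities) can be identified". It is NOT RELATED when its time course "rules out a causal relationship and another cause (eg, concomitant drugs, therapies, complications, comorbidities) is suspected". The text then adds that an AE is associated with the drug if "there is a reasonable possibility that the experience may have been caused by the drug".

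Several later steps use the category:

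- Protocol 7.2.1: "From EOT or ET through EOS, only AEs assessed as related to study drug by the Investigator (or designee) are to be reported". The follow-up call is made "to determine if any SAE or drug-related AE has occurred since the EOT or ET visit".
- Protocol 4.6, for withdrawn subjects: "AEs that are assessed as related to study drug and which are ongoing at ET may continue to be followed". Section 7.2.1 says the same at end of study, for AEs "assessed as related to study drug by the Investigator (or designee) which are ongoing at EOS may continue to be followed".
- Protocol 8.4 presents AE incidence by relationship. SAP 8.6.1 takes the investigator's category as the definition of a treatment-related TEAE.
- SAP 8.6.1 makes its rule for assigning TEAEs to the three treatments conditional on the event being judged related. It treats a missing relationship as related.
- Protocol Appendix 1, Reporting, makes an AE FDA-reportable when it is both associated with the drug and assessed as serious, related and unexpected.

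**The concern.** A two-category scale works only if every event falls in exactly one category. Here each category joins two conditions with *and*, so an event can satisfy one condition from each definition and belong to neither. The event most exposed is the ordinary ambiguous one, where the timing fits the drug but something else could also explain it.

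Such events are foreseeable in this trial. Protocol 1.4.1 records headache and nausea judged related to LOXO-305 in an earlier healthy-volunteer study. This study requires fasts of at least 10 hours before repaglinide dosing and bars caffeine from 72 hours before Check-in. A headache after dosing, with caffeine withdrawal identified as a possible explanation, is an illustration; the documents give no frequency for such events.

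Two investigators applying the same text could classify that headache differently. Between end of treatment (EOT) or early termination (ET) and end of study, a NOT RELATED choice for a non-serious event means it is not reported at all, so no later analysis could recover it.

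**Working it through.** The plan gives no figure to reproduce. The check is a full enumeration of the definitions.

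**Step 1. Timing by other cause, two levels each (2 × 2 = 4 combinations).**

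| Timing | Other cause | Category |
|---|---|---|
| Consistent | None | RELATED |
| Consistent | Present | Neither |
| Ruled out | None | Neither |
| Ruled out | Present | NOT RELATED |

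Two of the four are unassigned.

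**Step 2. Separate a suspected cause from an identified one (2 × 3 = 6 combinations).** The two definitions use different words: RELATED fails only if another cause can be identified, whereas NOT RELATED needs one only to be suspected.

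| Timing | No other cause | Suspected only | Identified |
|---|---|---|---|
| Consistent | RELATED | RELATED | **Neither** |
| Ruled out | **Neither** | NOT RELATED | NOT RELATED |

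Two of the six are unassigned. The lower one is harmless in practice, since an event whose timing excludes the drug would sensibly be NOT RELATED. The upper one, consistent timing with an identified alternative, is the substantive gap.

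**Step 3. Compare with the reasonable-possibility sentence.** That sentence does not require other causes to be absent. An event in the upper unassigned cell can therefore be associated with the drug and still be barred from RELATED. The Reporting text in Appendix 1 requires both, so such an event can pass one test and fail the other.

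**Step 4. Look for a default.** The SAP 8.6.1 default applies when the relationship is missing. It does not reach an event for which the investigator must choose a category and neither fits. Neither document gives another tie-break.

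**Step 5. Extent.**

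- The call takes place 7 ± 2 days after EOT or ET, so the related-only reporting window is 7 − 2 = 5 to 7 + 2 = 9 days. For a completer it runs from Day 16 to between Day 16 + 5 = Day 21 and Day 16 + 9 = Day 25.
- SAP 8.6.1 plans treatment-related TEAE summaries overall, by severity, by system organ class and preferred term, and by preferred term. All four use the category directly.
- The matching all-TEAE summaries are also by treatment. Because the assignment rule is worded for related events only, they cannot be called independent of the category on the literal text.
- Not affected: SAE notification (within 24 hours whatever the relationship), AE capture from Day 1 dosing to EOT or ET, TEAE status, the listing of all AEs, and the repaglinide PK comparison.

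**The case against.** The definitions are offered as guidelines, and the reasonable-possibility sentence could be read as the overriding test for anything they leave open. That is a fair reading, but the text does not state it. The Reporting paragraph treats association and relatedness as two separate requirements, which points the other way.

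The design should make the gap uncommon. Subjects are healthy and confined, and other medication is largely prohibited. For completers, the related-only window opens about five LOXO-305 half-lives after the last dose (Protocol 1.6), so few new events should have consistent timing. Follow-up of ongoing AEs is optional, and the sponsor makes the final SUSAR determination. All of this stands and limits the consequence. It does not close the gap: intercurrent illness, fasting and study procedures remain possible causes, and the half-life argument does not cover subjects who leave early.

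Some stronger readings are tempting but not supported:

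- *Any possible alternative cause leaves an event unclassified.* A cause that is only suspected can still sit within RELATED; the gap is exact only when the cause can be identified.
- *The protocol gives two contradictory definitions of relatedness.* It gives two thresholds, for association and for relatedness. They are in tension, but they do not define the same term.
- *Drug-related events will be undercounted.* Both definitions are strict, so the direction is unknown.
- *Events caused by repaglinide fall outside the assessment because the definitions say investigational product.* The lead-in says study drug, Protocol Table 3 and the Safety Population definitions include repaglinide, and SAP 8.6.1 assigns related events between Day 1 and Day 2 dosing to it. This is a loose term only.

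**Conclusion.** The point holds as a defect of definition with modest consequences. An AE with consistent timing and an identified alternative cause has no category, and RELATED is narrower than the causal standard stated in the same section. The effects stay within the secondary safety objective, for which SAP 8.6.6 plans no inferential analysis.

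The enumeration treats timing as either consistent or ruled out and reads the word *and* literally. The extension to assignment of TEAEs to treatments rests on the literal SAP wording; the authors may have meant the rule to cover all TEAEs. The protocol refers to further reporting instructions in a Study Manual that is not among the documents, so a default may exist there, although it would not remove the tension within Appendix 1.

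**What to change.** In Appendix 1, make the categories complements on the protocol's own standard:

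- RELATED: there is a reasonable possibility that study drug (repaglinide, LOXO-305, or both) caused the event, whether or not another possible cause exists.
- NOT RELATED: there is no such reasonable possibility.

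Keep time course and alternative causes as factors for the investigator to weigh, because reasonable possibility is not defined elsewhere and would give little guidance alone. Naming both drugs also settles the terminology. A stated default for mixed-cause events would close the gap too, but would leave RELATED narrower than the reasonable-possibility sentence unless that default were RELATED.

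The cost is a wording change in Appendix 1, carried into the AE form guidance. SAP methods do not change. The downside is that a few more non-serious events may be counted as related and recorded after EOT or ET.

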#### **Pregnancy**

As information is available, a pregnancy (including pregnancy in female partners of male subjects) diagnosed through EOS or ET (if the subject discontinues from the study and does not complete a follow-up phone call) and for up to 90 days after Day 12 (or last administration of study drug if subject terminates from the study early) should be reported by the Investigator (or designee) via email to Covance or the Sponsor's Clinical Safety Representative within 24 hours of being notified. Covance or the Sponsor's Clinical Safety Representative will then forward the Pregnancy Form to the Investigator (or designee) for completion.

